6.10 Concomitant Medication Assessments

A concomitant medication is any medication the subject enters the trial taking and is expected to continue taking for some portion of the trial, as well as any medication other than the investigational product that the subject takes during the course of the trial. All prescription and over-the-counter medications, including vitamins and herbal supplements, that subjects receive during the trial must be documented on the CRF. This documentation should continue until the subjects are discharged.

Concomitant medications will be coded using the World Health Organization Drug Dictionary (WHO-DD). A table of concomitant medications based on the anatomic therapeutic chemical classification (ATC) and preferred name will be produced. A listing of concomitant medications will include all medications taken by any subjects during the course of the study.

Concomitant medications administered during the study are to be recorded on the CRF. The medication name, dose, frequency, route of administration, date(s) of administration and reason for administration must be recorded. This documentation should continue until discharge from the study.

6.11 Removal of Subjects from the Trial or Study Drug

The investigator or designee must emphasize to potential subjects the importance of continued participation for the full duration of the trial during the informed consent process. Participation in the study is voluntary. A participant has the right to withdraw from the study at any moment for any reason. The investigator will be informed immediately.

The investigator has the right to terminate participation of a subject in case it is difficult to obtain blood samples, in case of violation of the protocol or in case of severe or serious adverse events.

In case a subject withdraws from the study, the study monitor will be informed immediately. If there is a medical reason for withdrawal, the volunteer should remain under the supervision of the medical investigator until satisfactory health returns.

Subjects who discontinue the active dosing phase of the study due to adverse event(s) or other safety concerns will not be replaced.

When the decision is made to discontinue a subject's participation in the study, no further investigational product medication should be administered. Every attempt should be made to complete all required study evaluations and procedures. Reasons for all withdrawals should be recorded on the CRF.

The investigator may withdraw a subject from the THR-1442-C-458 trial for any of the following reasons:

- A protocol violation occurs,
- A serious or intolerable adverse event occurs,
- A clinically significant change in a laboratory parameter occurs,
- The sponsor or investigator terminates the study, or
- The subject requests to be discontinued from the study.

Subjects who do not complete the study but who have received investigational product should have a follow-up examination, including a complete physical examination, vital signs, ECG and clinical laboratory tests if clinically indicated according to [Section 7](#).

6.12 Appropriateness of Measurements

PK parameters and safety assessments used in this study are standard assessments and are widely used and generally recognized as reliable, accurate, and relevant measurements.

Determination of urinary glucose is a non-invasive and quantitative method that allows immediate assessment of the PD effects of an SGLT2 inhibitor.

7 STUDY ACTIVITIES

7.1 Screening Visit (Days -21 to -1)

During the screening period, the following information will be gathered and the indicated procedures will be performed:

- Explain the content of informed consent to the subject and collect signed informed consent.
- Medical history and demographic information obtained.
- Perform a complete physical examination, including height and weight measurements as described in [Section 6.3](#).
- Vital signs collected including: pulse, temperature, respiratory rate, and blood pressure taken in the sitting position after at least 5 min of rest as described in [Section 6.4](#).
- 12-lead ECG taken in the supine position after at least 10 min of rest as described in [Section 6.5](#).
- Clean-catch, mid-stream urine will be collected for urinalysis as described in [Section 6.6.2.2](#). If urine is dipstick positive for leukocyte esterase or nitrites, sample is to be sent for microscopic evaluation and culture.
- Urine screen will be conducted for drug abuse and cotinine. If the drug screen is conducted more than 5 days pre-dose, the drug screen must be repeated prior to dosing.
- Drug abuse testing includes amphetamines, barbiturates, cocaine metabolites, opiates, benzodiazepines, Cotinine and cannabinoids.
- All female subjects will receive pregnancy test.
- Blood will be drawn for hematology, serum chemistry, and serology as detailed in [Section 6.6.2.1](#).
- The inclusion/exclusion criteria will be evaluated based on the information collected at the screening examination.

7.2 Clinic Admission (Day 0)

On day 0 the following information will be gathered and the indicated procedures will be performed:

- If screening was conducted more than five days prior to dosing, the inclusion and exclusion criteria must be confirmed and a urine drug screen performed.
- All female subjects will receive pregnancy test.
- Vital signs collected including: pulse, temperature, respiratory rate, and blood pressure taken in the sitting position after at least 5 min of rest as described in [Section 6.4](#).
- Perform 12-lead ECG taken in the supine position after at least 10 min of rest.
- Urinalysis will be collected as described in [Section 6.6.2.2](#). If urine is dipstick positive for leukocyte esterase or nitrites, sample is to be sent for microscopic evaluation and culture. Urine drug screen will be performed if drug screening is conducted more than 5 days prior to dosing.

- Blood will be drawn for hematology, and serum chemistry
- A partial physical examination must be performed as described in [Section 6.3](#).
- If the subject is still eligible based on the study inclusion and exclusion criteria the subject will be admitted and randomized into the study.
- Pre-dose urine collection in 12 h batches at -12 h to 0 h (on day 1) before bexagliflozin dosing for baseline analysis of creatinine and glucose for UGE (PD) analysis as described in [Section 6.6.2.2](#) and [Section 6.6.2.3](#).
- Concomitant medications and adverse event information will be collected as appropriate

7.3 Day 1 Activities: Groups 1 and 2 Pre-dose

Pre-dose blood glucose levels will be determined using a point-of-care blood glucose monitor. If the blood glucose levels are below 70 mg/dL, the study drug will not be administered. For subjects with pre-dose blood glucose levels < 70 mg/dL, oral glucose solution will be administered and once the subject's blood glucose is > 70 mg/dL, the study drug will be administered.

On day 1 the following information will be gathered and the indicated procedures will be performed PREDOSE (prior to whichever drug is taken first):

- Record vital signs pre-dose.
- Perform 12-lead ECG taken in the supine position after at least 10 min of rest pre-dose.
- Complete pre-dose urine collection at 0 h (-12 h to 0 h) before bexagliflozin dosing for baseline UGE analysis and analysis of creatinine as described in [Section 6.6.2.3](#).
- Pre-dose plasma samples will be drawn for PK analysis as detailed in [Section 6.6.2.4](#).
- Pre-dose concomitant medications and adverse event information collected as appropriate.

7.4 Day 1 Through 3 Activities: Group 1 Post-dose

On days 1 through 3 the following information will be gathered for group 1 subjects and the indicated procedures will be performed after dosing:

- Dosing with bexagliflozin tablets will occur 30 min before the start of the meal as detailed in [Section 5.2](#).
- Record vital signs at 4 h (day 1) and 48 h (day 3) postdose of bexagliflozin.
- Perform 12-lead ECG taken in the supine position after at least 10 min of rest at 4 h (day 1) postdose of bexagliflozin.
- Plasma samples will be drawn for PK analysis as detailed in [Section 6.6.2.4](#) at 0.5, 1, 2, 3, 4, 5, 6, 8, 10, 12, 16, 24, 36 (day 2) and 48 h (day 3) postdose of bexagliflozin.
- Urine collection in 12 h batches at 0 to 12 h and 12 to 24 h, 24 to 36 h and 36 to 48 h postdose of bexagliflozin for UGE analysis and analysis of creatinine as described in [Section 6.6.2.3](#).

- Postdose concomitant medications and adverse event information is collected as appropriate.
- On day 3 perform a partial physical examination as described in [Section 6.3](#).
- On day 3 urine will be collected as described in [Section 6.6.2.2](#) for urinalysis.
- On day 3 blood will be drawn for hematology and serum chemistry as detailed in [Section 6.6.2.1](#).
- After completion of all day 3 activities the subject will be discharged and scheduled to return to the clinical research unit on Day 7.

Subjects who are terminated from the study for any reason after dosing has started must have the information and procedures shown for day 10 collected and completed and the reason for termination entered onto the case report form.

7.5 Day 1 Through 3 Activities: Group 2 Post-dose

On days 1 through 3 the following information will be gathered for group 2 subjects and the indicated procedures will be performed after dosing:

- Dosing with first dose of subcutaneous exenatide 30 min prior to bexagliflozin tablets dosing will occur 1 h before the start of the breakfast as detailed in [Section 5.2](#).
- Dosing with second dose of subcutaneous exenatide 12 h after the first dose will occur 1 h before the start of the evening meal as detailed in [Section 5.2](#).
- Record vital signs at 4 h (day 1) and 48 h (day 3) postdose of bexagliflozin.
- Perform 12-lead ECG taken in the supine position after at least 10 min of rest at 4 h (day 1) postdose of bexagliflozin.
- Plasma samples will be drawn for PK analysis as detailed in [Section 6.6.2.4](#) at 0.5, 1, 2, 3, 4, 5, 6, 8, 10, 12, 16, 24, 36 (day 2) and 48 h (day 3) postdose of bexagliflozin.
- Urine collection in 12 h batches at 0 to 12 h and 12 to 24 h, 24 to 36 h and 36 to 48 h postdose of bexagliflozin for UGE analysis and analysis of creatinine as described in [Section 6.6.2.3](#).
- Postdose concomitant medications and adverse event information is collected as appropriate.
- On day 3 perform a partial physical examination as described in [Section 6.3](#).
- On day 3 urine will be collected as described in [Section 6.6.2.2](#) for urinalysis.
- On day 3 blood will be drawn for hematology and serum chemistry as detailed in [Section 6.6.2.1](#).
- After completion of all day 3 activities the subject will be discharged and scheduled to return to the clinical research unit on Day 7.

Subjects who are terminated from the study for any reason after dosing has started must have the information and procedures shown for day 10 collected and completed and the reason for termination entered onto the case report form.

7.6 Day 7 Activities: Groups 1 and 2

Pre-dose blood glucose levels will be determined using a point-of-care blood glucose monitor. If the blood glucose levels are below 70 mg/dL, the study drug will not be administered. For subjects with pre-dose blood glucose levels < 70 mg/dL, oral glucose solution will be administered and once the subject's blood glucose is > 70 mg/dL, the study drug will be administered.

On day 7 the following information will be gathered and the indicated procedures will be performed:

- If the subject is still eligible based on the study inclusion and exclusion criteria, the subject will be admitted for the cross-over phase of the study.
- Record vital signs.
- Perform 12-lead ECG taken in the supine position after at least 10 min of rest.
- Urine drug screen and clean catch urinalysis will be collected as described in [Section 6.6.2.2](#). If urine is dipstick positive for leukocyte esterase or nitrites, sample is to be sent for microscopic evaluation and culture.
- All female subjects will receive pregnancy test.
- Blood will be drawn for hematology, and serum chemistry
- Perform a partial physical examination as described in [Section 6.3](#).
- Pre-dose urine collection in 12 h batches at -12 h to 0 h (on day 1) before bexagliflozin dosing for baseline analysis of creatinine and glucose for UGE (PD) analysis as described in [Section 6.6.2.2](#) and [Section 6.6.2.3](#).
- Concomitant medications and adverse event information will be collected as appropriate.

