1.2 Glucagon-like peptide 1 receptor agonists (GLP-1 RAs) and Exenatide

GLP-1 RAs are recommended as an option in patients with T2DM, typically as a second-line agent, particularly when weight loss or avoidance of hypoglycemia is a primary consideration in the therapeutic strategy. GLP-1 RAs reduce hyperglycemia and promote weight loss by enhancing glucose-dependent insulin secretion, suppressing postprandial glucagon release, signaling satiety, and slowing gastric emptying. In terms of safety, the most common adverse events seen in clinical trials with GLP-1 RAs are of gastrointestinal character; mainly nausea, vomiting and diarrhea. However, the incidence diminishes over time. Other identified risks include pancreatitis, immunogenicity, acute renal failure and

rapid weight loss. Exenatide is one of most widely prescribed GLP-1 RAs. It was approved in 2005 and is administered subcutaneously bid at a maximum approved dose in the United States of 10 µg. It is recommended to be taken within 60 minutes of the morning meal and within 60 minutes of the evening meal (approximately 6 hours or more apart).

After subcutaneous administration, exenatide is rapidly absorbed, usually reaching peak concentrations 2 h post administration. Peak plasma concentrations of exenatide after a 10 µg dose reach approximately 200 pg/mL. Exenatide is primarily eliminated by glomerular filtration and subsequent proteolytic degradation. After a single subcutaneous dose, it exhibits a short half-life of approximately 2.4 h. PK/PD modeling and empirical assessments from early clinical studies supported a twice daily dosing regimen. Because of its relatively short half-life, significant systemic accumulation is not observed with repeated twice-daily dosing.

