5.2 Treatment(s) Administered

Approximately 20 eligible healthy subjects will be randomly assigned to one of the two groups (1 or 2) with up to 10 subjects per group. Each group will receive both the treatments alternately, in a crossover fashion (two-period, two-treatment crossover design), with the two treatment periods separated by a 7-day washout period. In Treatment Period 1, subjects in Group 1 will receive a single oral dose of bexagliflozin tablets, 20 mg, alone 30 min before breakfast, and subjects in Group 2 will receive subcutaneous injection dose of exenatide at 10 µg bid with initial dosing 30 min prior to a single oral dose of bexagliflozin tablets, 20 mg, and 1 h before breakfast and followed by the second dosing of exenatide alone 1 h prior to evening meals. In Treatment Period 2, subjects in Group 1 will receive subcutaneous injection dose of exenatide at 10 µg bid with initial dosing 30 min prior to a single oral dose of bexagliflozin tablets, 20 mg, and 1 h before breakfast and followed by the second dosing of exenatide alone 1 h prior to evening meals and subjects in Group 2 will receive a single oral dose of bexagliflozin tablets, 20 mg, alone 30 min before breakfast.

The detailed dosing schedule is shown in [Table 1](#).

Table 1. Dosing Schedule

Subject Group	Treatment Period Dosing Time (h)	Treatment Period 1(Day 1)						Treatment Period 2 (Day 8)					
		0	0.5	1	4-6	9	10	0	0.5	1	4-6	9	10
Group 1	Bexagliflozin tablets, 20 mg		X						X				
	Single oral dose												
	Exenatide at 10 µg bid								X				X
	SC Meal			X	X		X			X	X		X
Group 2	Bexagliflozin tablets, 20 mg		X						X				
	Single oral dose												
	Exenatide at 10 µg bid	X					X						
	SC Meal			X	X		X			X	X		X

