9.6 Pharmacodynamic Assessments

UGE and urinary creatinine will be assessed before first dosing and at the end of each treatment period.

UGE, including UGE_{t1-t2} and the total 0-24, 24-48 and 0-48 h UGE, will be determined. UGE_{t1-t2} (mg) will be derived from urine volume (V_{t1-t2}, mL) × glucose concentration (mg/dL) ÷ 100. Parameters normalized for urinary creatinine excretion will also be determined. UGE_{0-12h}, UGE_{12-24h}, UGE_{24-36h}, UGE_{36-48h} and the total 48 h UGE will be listed and presented in by subject listing and in summary tables for each group.

UGE in 12 h intervals up to 48 h post-dose, including the baseline, will be graphically presented against the corresponding treatment, bexagliflozin alone, and combination with exenatide.

The descriptive statistics will be used to describe any differences in UGE values between treatment groups.

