5.3 Pharmacodynamic Population

The PD Population will include all randomized subjects who receive study drug and have had 0-12 hr and 12 to 24 hr urine collection from which to calculate 24-hour UGE following dosing. The PD Population will be used to summarize the PD parameters. Subjects will be analyzed according to the treatment received.

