7.3 Pharmacodynamic Analyses

Urinary glucose excretion will be determined as a PD parameter at baseline and up to 48 hours.

Descriptive statistics of glucose concentrations, creatinine concentrations, UGE, and urinary glucose/urinary creatinine will be summarized by Treatment and Timepoint.

The quantity of glucose excreted in urine will be determined by multiplying the urine glucose concentration for each time interval by the volume of urine collected for the corresponding collection interval. The total 24-hour and 48-hour quantity of glucose excreted in urine will be calculated by adding the amounts collected during each interval.

PD data will also be reported in listings.

The PD parameters, UGE and UGE normalized by urinary creatinine, including $UGE_{t_1-t_2}$, in 12 hour and 24 hour increments, and total 24-hour and 48-hour UGE, will be determined. $UGE_{t_1-t_2}$ (g) will be derived from urine volume ($V_{t_1-t_2}$, mL) x glucose concentration (mg/dL)/100/1000.

UGE normalized by urinary creatinine will be derived by dividing the UGE for each interval by the corresponding urinary creatinine concentration.

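### The protocol gives two clocks for the second exenatide dose and dinner: Sections 7.5 and 7.8 say 12 h and 13 h, but Table 1 stops at 10 h

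*Protocol*

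**What the plan says.** - **Protocol 7.5 (Group 2, Period 1) and 7.8 (Group 1, Period 2).** Both sections cover the combination treatment and carry the same instruction: "Dosing with second dose of subcutaneous exenatide 12 h after the first dose will occur 1 h before the start of the evening meal". Both point to Section 5.2 for the detail.
- **Protocol 5.2, text.** The second injection is tied to the meal only: "followed by the second dosing of exenatide alone 1 h prior to evening meals". No interval from the first injection is given, and the reader is sent to Table 1 for the detailed schedule.
- **Protocol 5.2, Table 1.** The time columns are 0, 0.5, 1, 4-6, 9 and 10 h, the same in both periods. Meals are marked at 1, 4-6 and 10 h for both groups in both periods.
- **Protocol 7.4 and 7.9 (bexagliflozin alone).** Only breakfast is timed: "Dosing with bexagliflozin tablets will occur 30 min before the start of the meal". Neither section gives a dinner time.
- **UGE reporting.** Protocol 9.6: "UGE in 12 h intervals up to 48 h post-dose, including the baseline, will be graphically presented against the corresponding treatment". SAP 7.3 lists UGE "in 12 hour and 24 hour increments, and total 24-hour and 48-hour UGE, will be determined". The SAP 5.3 PD population needs subjects who "have had 0-12 hr and 12 to 24 hr urine collection from which to calculate 24-hour UGE following dosing".

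**The concern.** The combination regimen has two dosing clocks that disagree, and a site that follows one departs from the other. The morning doses are the same on both, so the discrepancy concerns the evening injection and the evening meal.

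It matters because the effect of exenatide on the PD of bexagliflozin is part of the primary objective (Protocol 2.1), and UGE is summarized by treatment in 12-h batches. One clock places dinner before the 12-h boundary and the other places it after. If staff followed Sections 7.5 and 7.8 for the combination and Table 1 for bexagliflozin alone, dinner would be 3 h later in the combination treatment. The comparison of UGE at 0-12 h and 12-24 h would then mix the effect of exenatide with the effect of meal timing.

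**Working it through.** **Time zero.** Section 5.2 gives exenatide 30 min before bexagliflozin and 1 h before breakfast. Table 1 marks bexagliflozin at 0.5 h and breakfast at 1 h, so 0 h is the first exenatide injection. Time after bexagliflozin is therefore the Table 1 time minus 0.5 h.

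**What can be read from Table 1.** The extracted exenatide marks look shifted. Group 1's first dose in Period 2 appears under 0.5 h, and the second dose appears under 10 h, the meal column, for both groups. These positions are not treated as errors in the plan. The check uses the column headings and the meal rows, which agree across all four group-period cells. The breakfast mark at 1 h also matches the text. A second dose at 9 h is inferred: the text puts it 1 h before a 10 h meal, and the 9 h column holds no other event.

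**The two clocks**

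| Event | Sections 7.5/7.8 | Table 1 with the 1-h rule | Gap |
|---|---|---|---|
| Second exenatide dose | 12 h | 10 - 1 = 9 h (inferred) | 12 - 9 = 3 h |
| Dinner | 12 + 1 = 13 h | 10 h | 13 - 10 = 3 h |
| Second dose after bexagliflozin | 12 - 0.5 = 11.5 h | 9 - 0.5 = 8.5 h | 3 h |
| Dinner after bexagliflozin | 13 - 0.5 = 12.5 h | 10 - 0.5 = 9.5 h | 3 h |
| Second exenatide peak after bexagliflozin (about 2 h after injection, Protocol 1.2) | 11.5 + 2 = 13.5 h | 8.5 + 2 = 10.5 h | 3 h |

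**Other readings tried**
- Second-dose mark taken literally at 10 h: the dose conflict is 12 - 10 = 2 h and the dinner conflict is still 3 h.
- Time zero taken as bexagliflozin dosing: Sections 7.5 and 7.8 give 11.5 h and 12.5 h, still past the last column.

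No reading of Table 1 gives a second dose 12 h after the first.

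**Share of the 0-12 h urine batch, in clock time**
- After dinner: (12 - 9.5)/12 = 20.8% under Table 1; 0% under 7.5/7.8, where dinner at 12.5 h falls after the batch closes.
- After the second exenatide dose: (12 - 8.5)/12 = 29.2% under Table 1 (inferred 9 h dose); (12 - 11.5)/12 = 4.2% under 7.5/7.8.

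**Search for a resolving rule.** Protocol 5.3 and SAP Sections 1 and 3.1 repeat only the 1-h rule. Protocol 5.7.2 gives no dinner time. Protocol 1.2 describes the two daily exenatide doses as "approximately 6 hours or more apart", which both intervals satisfy. No dosing window or order of precedence is stated.

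**The case against.** The strongest reply is that this is a small editorial slip. The 12-h figure appears only in two activity bullets that defer to Section 5.2, so Table 1 could be read as controlling and 12 h as a loose rendering of twice-daily dosing. Table 1 already shows the same meal times for both treatments. UGE is described, not tested (SAP 3.3), and the 80-125% limits apply only to Cmax and the two AUCs. Bexagliflozin tmax is 3 to 5 h (Protocol 1.1.2), before the second injection on either clock. Dosing is supervised and exact dosing times are recorded (Protocol 5.8), so the actual second-dose time will be known. Finally, the percentages above are shares of clock time, not of glucose excreted.

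Much of this stands and limits the size of the point. The effect is confined to the 12-h split, and bias requires unequal dinner times. The 9 h dose is an inference from a poorly extracted table.

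The conflict itself is not removed. Reading Table 1 as controlling is plausible, but the protocol does not say so, and the activity sections give an explicit 12 h figure. Recording dosing times shows afterwards what was done; it does not tell the site what to do. It also captures no dinner time for bexagliflozin alone, where there is no second injection from which to infer one.

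**Conclusion.** The concern holds. Sections 7.5 and 7.8 cannot be reconciled with Table 1. Dinner differs by 3 h on either reading of the table; the second dose differs by 3 h as inferred, or by 2 h if the extracted mark is taken literally. The internal inconsistency should be fixed because it sits in operative dosing text and crosses the 12-h boundary of a PD measure in the primary objective.

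The likely consequence is modest. UGE could move between the 0-12 h and 12-24 h batches, and the treatment comparison of that split would be biased only if dinner times differed between treatments. The documents give no UGE rate by time of day, so the shift in grams cannot be stated. Cmax and the 0-24 h and 0-48 h UGE totals should be little affected. No AUC effect and no safety issue is claimed. The conclusion rests on Table 1's column headings and meal rows having been extracted correctly.

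**What to change.** 1. Choose one clock and make Sections 7.5, 7.8 and Table 1 agree. Either change the interval in 7.5 and 7.8 to 9 h, with dinner at 10 h, or change the last two Table 1 columns from 9 and 10 h to 12 and 13 h.
2. State that dinner is served at the same time relative to bexagliflozin in both treatments and both periods, and add that time to Sections 7.4 and 7.9.
3. Optionally, record the actual dinner time.

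The cost is a wording correction, plus one case report form entry per period if dinner time is recorded. No visits, samples or subjects are added.

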3 INVESTIGATIONAL PLAN

3.1 Overall Study Design and Plan

This single center, phase 1, open-label, 2×2 crossover study is designed to assess the effects of exenatide injection on the PK and PD of orally administered bexagliflozin tablets. Approximately 20 eligible healthy subjects will be randomly assigned to one of the two groups (1 or 2) with up to 10 subjects per group. Each group will receive both the treatments alternately, in a crossover fashion (two-period, two-treatment crossover design), with the two treatment periods separated by a 7-day washout period. In Treatment Period 1, subjects in Group 1 will receive a single oral dose of bexagliflozin tablets, 20 mg, alone 30 min before breakfast, and subjects in Group 2 will receive subcutaneous injection dose of exenatide at 10 μg bid with initial dosing 30 min prior to a single oral dose of bexagliflozin tablets, 20 mg, and 1 h before breakfast and followed by the second dosing of exenatide alone 1 h prior to evening meals. In Treatment Period 2, subjects in Group 1 will receive subcutaneous injection dose of exenatide at 10 μg bid with initial dosing 30 min prior to a single oral dose of bexagliflozin tablets, 20 mg, and 1 h before breakfast and followed by the second dosing of exenatide alone 1 h prior to evening meals and subjects in Group 2 will receive a single oral dose of bexagliflozin tablets, 20 mg, alone 30 min before breakfast.

Clinical laboratory tests and safety monitoring will be conducted during both treatment periods.

In treatment period 1, subjects will be admitted to the clinic on day 0, the day before dosing, and will stay in the clinic until 48 h post-dose. In treatment period 2, subjects will be admitted to the clinic on day 7, the day before dosing, and will stay in the clinic until 48 h post-dose. Blood samples for bexagliflozin plasma concentrations will be collected at each period at pre-dose and at 0.5, 1, 2, 3, 4, 5, 6, 8, 10, 12, 16, 24, 36, and 48 h post-dose of bexagliflozin.

Urine samples for PD analysis will be collected at each period in 12 h batch at pre-dose (h - 12 to 0), and at post-dose of bexagliflozin at 0 to 12 h, 12 to 24 h, 24 to 36 h, and 36 to 48 h.

Sampling time was determined based on previous pilot PK and PD studies.

For the schedule of study events table, see [Appendix 1](#). For overall dosing schedule, see [Table 1](#).

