5.7.2 Fluid and Food Intake

An overnight fast of at least 10 h prior to dosing is required. Bexagliflozin tablets will be taken in the morning with 240 mL of water prior to any drinking or eating.

Water can be allowed as desired except for one hour before and after drug administration. Water can be allowed during breakfast on D1 and D8.

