6.9.4.4 Hypoglycemia

Hypoglycemia will be recorded under 5 categories:

- Critical hypoglycemia: An event requiring assistance of another person to actively administer carbohydrate, glucagons, or other resuscitative actions. These episodes may be associated with sufficient neuroglycopenia to induce seizure or coma. Plasma glucose

measurements may not be available during such an event, but neurological recovery attributable to the restoration of plasma glucose to normal is considered sufficient evidence that the event was induced by a low plasma glucose concentration. All such events should be recorded as serious adverse events in the CRF.

- Documented symptomatic hypoglycemia: An event during which typical symptoms of hypoglycemia are accompanied by a measured plasma glucose concentration ≤ 70 mg/dL (3.9 mmol/L).
- Asymptomatic hypoglycemia: An event not accompanied by typical symptoms of hypoglycemia but with a measured plasma glucose concentration ≤ 70 mg/dL (3.9 mmol/L).
- Probable symptomatic hypoglycemia: An event during which symptoms of hypoglycemia are not accompanied by a plasma glucose determination but that was presumably caused by a plasma glucose concentration ≤ 70 mg/dL (3.9 mmol/L).
- Relative hypoglycemia: An event during which the subjects report any of the typical symptoms of hypoglycemia, and interprets those as indicative of hypoglycemia, but with a measured plasma glucose concentration > 70 mg/dL (3.9 mmol/L).

If a subject experiences symptomatic hypoglycemia, confirmed by point-of-care glucose monitoring at the time of symptoms with a blood sugar level < 70 mg/dL (3.9 mmol/L), the subject should be treated with 15 to 20 grams of oral glucose or simple carbohydrate (glucose tablets, raisins, orange juice, glucose-containing soda, or soft sugar candies).

If a subject with symptomatic hypoglycemia is unable to self-administer glucose tablets, candies, or glucose-containing solutions, then the appropriate study staff should administer either intramuscularly or subcutaneously a single injection of 1.0 mg of glucagon. A single dose of glucagon should restore consciousness within approximately fifteen minutes. Failure to correct hypoglycemia within this timeframe or observation by appropriate study staff of profound low sugar with accompanying coma or seizure will be treated by intravenous infusion of 5% dextrose.

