7.7 Day 8 Activities: Groups 1 and 2 Pre-dose

On day 8 the following information will be gathered and the indicated procedures will be performed PREDOSE:

- Record vital signs pre-dose.
- Perform 12-lead ECG taken in the supine position after at least 10 min of rest pre-dose.
- Complete pre-dose urine collection at 0 h (-12 h to 0 h) before bexagliflozin dosing for baseline UGE analysis and analysis of creatinine as described in [Section 6.6.2.3](#).
- Pre-dose plasma samples will be drawn for PK analysis as detailed in [Section 6.6.2.4](#).
- Pre-dose concomitant medications and adverse event information collected as appropriate.

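### The Period 2 pre-dose glucose check and dosing hold is printed under Day 7, when nothing is dosed, and is missing from the Day 8 pre-dose section

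*Protocol*

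**What the plan says.** Section 7.3 (Day 1, pre-dose) opens with a paragraph on point-of-care glucose. A subject below 70 mg/dL is not dosed; instead, "oral glucose solution will be administered and once the subject's blood glucose is > 70 mg/dL, the study drug will be administered". The same paragraph opens Section 7.6, which is headed Day 7.

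Day 7 is an admission day. Protocol Section 3.1 states that in Period 2 "subjects will be admitted to the clinic on day 7, the day before dosing", and Table 1 in Section 5.2 places every Period 2 dose on Day 8.

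Section 7.7 covers the dosing morning itself: "On day 8 the following information will be gathered and the indicated procedures will be performed PREDOSE". Its list has five items: vital signs, ECG, completion of the baseline urine collection, the PK sample, and concomitant medication and adverse events. Glucose is not among them, and the Day 8 to 10 post-dose sections (7.8 and 7.9) do not add it.

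Section 5.7.2 sets the fasting rule: "An overnight fast of at least 10 h prior to dosing is required".

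**The concern.** The hold is the protocol's own safeguard against dosing a fasted subject whose glucose is already low. It can work only if the reading is taken on the morning of dosing. Under Day 7 there is no dose to withhold, and a reading that day comes before the overnight fast that leads into Day 8 dosing. Day 7 also already has a serum chemistry draw that includes glucose, so a point-of-care reading there adds little.

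A site that builds its worksheets from the section headings could therefore do the check on Day 7 and have nothing on its Day 8 worksheet. On Day 8, Group 1 receives exenatide 1 h before breakfast, with bexagliflozin 30 min after the injection. Group 2 receives bexagliflozin 30 min before breakfast. What is at stake is participant protection on those mornings.

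**Working it through.** **Placement.** The relevant sections, side by side:

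| Protocol section | Day | Drug given that day? | Glucose check and hold printed? |
|---|---|---|---|
| 7.2 | 0 (Period 1 admission) | No | No |
| 7.3 | 1, pre-dose | Yes | Yes |
| 7.6 | 7 (Period 2 admission) | No | Yes |
| 7.7 | 8, pre-dose | Yes | No |

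In Period 1 the check is tied to the dosing day and not to the admission day. Period 2 reverses this, and nothing in the protocol gives a reason. Section 7.6 also carries another sign of copying, since its urine item reads "Pre-dose urine collection in 12 h batches at -12 h to 0 h (on day 1) before bexagliflozin dosing" although it belongs to Period 2. A misplaced paragraph explains both.

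**Does anything else fix the day?**

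- Appendix 1 of the protocol has no point-of-care glucose row or footnote for any day, so it cannot settle the matter. This is equally true of Day 1, where the text is correctly placed. The absent row is therefore not itself a Period 2 error.
- Laboratory draws are at screening and on Days 0, 3, 7 and 10. None falls on Day 8.
- In Section 6.9.4.4 the treatment step begins from symptoms: "If a subject experiences symptomatic hypoglycemia, confirmed by point-of-care glucose monitoring at the time of symptoms". The repeat monitoring begins once hypoglycemia has been detected. Neither is a pre-dose screen.

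**Count of dosing mornings.** Inputs: 20 subjects allocated 1:1 (Sections 4.1 and 5.4), hence 10 per group, and two periods.

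- The plan's own figure (Section 9.7.1) is 20 subjects dosed with bexagliflozin alone and 20 with the combination. Reproduced: 10 + 10 = 20 for each treatment, and 20 + 20 = 40 dosing mornings.
- Day 1, covered by Section 7.3: 2 groups × 10 = 20.
- Day 8, with no check printed for that day: 2 × 10 = 20, made up of 10 combination doses (Group 1) and 10 bexagliflozin-alone doses (Group 2).
- Coverage if the headings are followed strictly: 20/40 = 50%. If only 18 or 16 subjects reach Period 2 without replacement, it is 20/38 = 53% or 20/36 = 56%.
- Coverage if staff infer Day 8, or after the paragraph is moved: 40/40.
- Share uncovered by treatment under the strict reading: 10/20 = 50% for the combination and 10/20 = 50% for bexagliflozin alone.

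The count is of mornings, not of subjects harmed. The documents give no frequency of fasting glucose below 70 mg/dL in such subjects, so the number who would be held cannot be estimated.

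**The case against.** The strongest reply is that the paragraph explains itself. It speaks of pre-dose levels and of giving the study drug afterwards, which makes sense only on a dosing morning. It stands above the sentence that introduces the Day 7 list, and it names no day. Section 7.6 also already contains a task that runs into Day 8, the 12-hour baseline urine collection.

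This largely stands. It makes Day 8 by far the more likely reading, and it rules out two stronger conclusions that a reader might draw. One is that half the dosing mornings are unprotected as a matter of fact; that is so only under the strict heading-based reading. The other is that a site could dose a subject known to be below 70 mg/dL on Day 8 without deviating; the prohibition has no day limit, so the documents do not support that. What remains is that the prohibition needs a reading to act on, and no text asks for one on Day 8.

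A reader might also infer that Section 7.3 already requires the glucose check before the first drug of the morning. The relevant words are in the lead-in "On day 1 the following information will be gathered and the indicated procedures will be performed PREDOSE (prior to whichever drug is taken first", which introduces the bulleted procedures. The glucose paragraph stands above that lead-in and is not governed by it. Stating the order for the glucose check would be a clarification, not a restoration.

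Finally, the risk is small. The protocol's Introduction describes both drug classes as carrying little risk of hypoglycemia. Subjects are healthy, a history of hypoglycemia is an exclusion, dosing is supervised in the clinic, and breakfast follows within 30 to 60 min of the first drug. All of this stands and limits the weight of the point. It does not explain why a check wanted on Day 1 should be left to inference on Day 8, when the fasting and meal conditions are the same.

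**Conclusion.** The point holds as a misplaced safety rule. The check and hold are printed under a day with no dosing and are absent from the section for the dosing morning. The intended day is almost certainly Day 8, but no other passage or schedule confirms it.

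The size is between 0 and 20 of the 40 planned dosing mornings without a same-day check: 0 if staff infer Day 8, 20 if the section headings are followed strictly. This assumes 10 subjects per group who all reach Period 2.

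It would be wrong to infer a bias in the results. Under the strict reading the uncovered mornings fall equally on the two treatments, and no effect on the PK, PD or adverse event comparison is claimed. Nor is the SAP at fault: it defines no point-of-care glucose variable and is read together with the protocol.

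**What to change.** 1. Move the glucose paragraph from Section 7.6 to Section 7.7.
2. In both Sections 7.3 and 7.7, state that the reading is taken before the first drug of the morning. For the combination treatment that drug is exenatide.
3. Optionally, add a point-of-care glucose row to protocol Appendix 1, marked at Day 1 pre-dose and Day 8 pre-dose. No change to the SAP is needed.

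The cost is one moved paragraph, a short sentence in two sections and, if wanted, one table row. In conduct it means one point-of-care reading per subject on Day 8, 20 in all; at a site that had been testing on Day 7, these replace the Day 7 readings. An occasional Period 2 dose may be delayed or preceded by oral glucose, which Section 7.3 already accepts on Day 1.
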